2.1.1 General definitions

2.1.1.1 Treatment groups

In the final analysis, the summaries by treatment will be performed by the treatment sequence.

- Treatment sequence:

- AIN457 150 mg – AIN457 150 mg
- AIN457 150 mg – AIN457 [REDACTED]
- Placebo – AIN457 150 mg
- Placebo – AIN457 [REDACTED]

For some safety summaries (e.g., exposure-adjusted) the ‘switch’ treatment may be summarized separately:

- Entire study: Placebo, Any AIN457 150 mg, Any AIN457 [REDACTED], Any AIN457.

In the safety and efficacy listings, the groups will be presented by treatment sequence.

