2.1.1.3 Screening, baseline and post-baseline definitions

Screening refers to any procedures (e.g., checking inclusion and exclusion criteria) performed prior to the date of first dose of study treatment (for safety analysis) or prior to the randomization date (for efficacy analysis). Per protocol, subject informed consent must be obtained prior to performing any study related activity. The date of signing informed consent is the start date of screening period. Any assessment obtained during the screening period will be labeled screening assessment. Assessments made on Day 1 may occur before or after the randomization or the first dose. Further information will be found in Programming Datasets Specifications (PDS).

For efficacy analyses, baseline is the last assessment (including unscheduled visits) obtained (on or) before randomization (day). All assessments obtained after randomization (day) are considered as post-baseline unless otherwise specified.

For safety analyses, baseline is the last assessment (including unscheduled visits) obtained (on or) before the first dose of study treatment. All assessments obtained after the first dose (day) of study treatment are considered as post-baseline unless otherwise specified.

Of note, baseline will be derived based on the randomization day or first dose day, exact randomization/dosing time is not considered.

In general, a baseline value refers to the last measurement made prior to administration of the first dose of study treatment. However, for patient reported outcomes, laboratory assessments and ECG if no pre-treatment value exists, values obtained after first dose of treatment can be used as baseline only if it was collected on the same day as first dose.

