2.7.1 Adverse events (AEs)

Treatment-emergent adverse events (i.e., events started after the first dose of study treatment or events present prior to the first dose of study treatment but increased in severity based on preferred term and on or before last dose + 84 days) will be summarized.

Adverse events will be summarized by presenting, for each treatment group, the number and percentage of participants having any AE, having an AE in each primary system organ class and having each individual AE (preferred term). Summaries will also be presented for AEs by severity and for study treatment related AEs. If a participant reported more than one adverse event with the same preferred term, the adverse event with the greatest severity will be presented. If a participant reported more than one adverse event within the same primary system organ class, the participant will be counted only once with the greatest severity at the system organ class level, where applicable. Serious adverse events will also be summarized.

These summaries may be presented separately by placebo controlled period and entire study.

As appropriate, the incidence of AEs will be presented per 100 patient years of exposure (exposure-adjusted incidence rates).

Separate summaries will be provided for death, serious adverse event, other significant adverse events leading to discontinuation and adverse events leading to dose adjustment (including study treatment discontinuation).

A graphical display of relative frequencies within system organ classes and relative risks, as appropriate, will be presented.

Adverse events will also be reported separately by Standardized MedDRA Query (SMQ) according to MedDRA. The MedDRA version used for reporting the study will be described in a footnote.

Treatment emergent and non-treatment emergent adverse events will be listed.

Algorithms for date imputations will be provided in Programming Datasets Specifications.

For serious adverse events (SAEs) occurred during screening a listing were prepared for all subjects screened including screening failures at the primary endpoint analysis.

The safety analysis that will be performed for treatment emergent AEs and on treatment labs and vital signs for each analysis period is described in Table 2-1.

The data in the period of Day 1 – Week 16 were presented at the primary endpoint analysis; the data in the period of Entire treatment will be presented at the Final Analysis.

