Neutrophil count decreased	<LLN - 1.5 x 10e9 /L	<1.5 - 1.0 x 10e9 /L	<1.0 - 0.5 x 10e9 /L	<0.5 x 10e9 /L
Lymphocyte count decreased	<LLN - 0.8 x 10e9/L	<0.8 - 0.5 x 10e9 /L	<0.5 - 0.2 x 10e9 /L	<0.2 x 10e9 /L
Creatinine increased*	>1 - 1.5 x baseline; >ULN - 1.5 x ULN	>1.5 - 3.0 x baseline; >1.5 - 3.0 x ULN	>3.0 baseline; >3.0 - 6.0 x ULN	>6.0 x ULN
TBL increased	>ULN - 1.5 x ULN	>1.5 - 3.0 x ULN	>3.0 - 10.0 x ULN	>10.0 x ULN
GGT increased	>ULN - 2.5 x ULN	>2.5 - 5.0 x ULN	>5.0 - 20.0 x ULN	>20.0 x ULN
ALT increased	>ULN - 3.0 x ULN	>3.0 - 5.0 x ULN	>5.0 - 20.0 x ULN	>20.0 x ULN
AST increased	>ULN - 3.0 x ULN	>3.0 - 5.0 x ULN	>5.0 - 20.0 x ULN	>20.0 x ULN
ALP increased	>ULN - 2.5 x ULN	>2.5 - 5.0 x ULN	>5.0 - 20.0 x ULN	>20.0 x ULN
Glucose increased (Hyperglycemia)	>ULN - 8.9 mmol/L	>8.9 - 13.9 mmol/L	>13.9 - 27.8 mmol/L	>27.8 mmol/L
Glucose decreased (Hypoglycemia)	<LLN - 3.0 mmol/L	<3.0 - 2.2 mmol/L >7.75 - 10.34 mmol/L	<2.2 - 1.7 mmol/L >10.34 - 12.92 mmol/L	<1.7 mmol/L
Cholesterol high	>ULN - 7.75 mmol/L			>12.92 mmol/L
Hypertriglyceridemia	1.71 - 3.42 mmol/L	>3.42 - 5.7mmol/L	>5.7 - 11.4 mmol/L	>11.4 mmol/L

* Note: for "creatinine increased" the baseline criteria do not apply

Shift tables will be presented comparing baseline laboratory result (CTCAE grade) with the worst results (expressed in CTCAE grade) during the treatment phase (either initial up to week 16 or entire) analyzed. Of note, baseline will be defined as last assessment prior to first dosing in initial treatment phase.

Summaries for newly occurring or worsening clinically notable lipid abnormalities will also be provided cumulatively for each of the following parameters and categories:

- HDL:
 - <=LLN
 - <0.8x LLN
- LDL, cholesterol, triglycerides:
 - >=UNL
 - >1.5 x ULN

- > 2.5 x ULN

Newly occurring or worsening liver enzyme abnormalities will also be summarized based on the event criteria given in Table 2-3:

Table 2-3 Liver-related events

Parameter	Criterion
ALT	>3xULN; >5xULN; >8xULN; >10xULN, >20xULN
AST	>3xULN; >5xULN; >8xULN >10xULN; >20xULN
ALT or AST	>3xULN; >5xULN; >8xULN >10xULN; >20xULN
TBL	>1.5xULN; >2xULN; >3xULN
ALP	>2xULN; >3xULN; >5xULN
ALT or AST & TBL	ALT or AST >3xULN & TBL >2xULN; ALT or AST >5xULN & TBL >2xULN; ALT or AST >8xULN & TBL >2xULN; ALT or AST >10xULN & TBL >2xULN;
ALP & TBL	ALP >3xULN & TBL >2xULN ALP >5xULN & TBL >2xULN

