2.7.4 Other safety data

2.7.4.1 ECG and cardiac imaging data

The summary of ECG will only include treatment emergent data, which are defined as those ECG measurements after the first dose of study treatment and on or before last dose + 84 days.

Analysis in ECG parameters using descriptive summary statistics for the change from baseline for each post-baseline visit will be performed. These descriptive summaries will be presented by ECG parameter and treatment group. Change from baseline will only be summarized for subjects with both baseline and post-baseline values and will be calculated as:

Change from baseline = post-BSL - BSL

The following quantitative variables will be summarized: ECG mean heart rate, RR interval, PR interval, QRS duration, QT interval, and corrected QT interval (QTc). Fridericia (QTcF) corrections will be presented for QTc.

QTc will be summarized by computing the number and percentage of subjects (including 95% confidence intervals for pooled analysis, e.g., DMC or SCS) with:

- QTcF > 500 msec
- QTcF > 480 msec
- QTcF > 450 msec
- QTcF changes from baseline > 30 msec
- QTcF changes from baseline > 60 msec
- PR > 250 msec

Summary statistics will be presented for ECG variables by visit and treatment group.

In addition, shift tables comparing baseline ECG interpretation (normal, abnormal, not available, total) with the worst on-study interpretation (normal, abnormal, not available, total) will be provided.

A listing of all newly occurring or worsening abnormalities will be provided, as well as a by-subject listing of all quantitative ECG parameters.

Qualitative changes will be summarized.

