2.7.4.2 Vital signs

The summary of vital signs will only include on treatment data, which are defined as those vital sign measurements after the first dose of study treatment and on or before last dose + 84 days.

Analysis of the vital sign measurements using summary statistics for the change from BSL for each post-BSL visit will be performed. These descriptive summaries will be presented by vital sign and treatment group. Change from BSL will only be summarized for participants with both BSL and post-BSL values and will be calculated as:

change from BSL = post-BSL – BSL

the number and percentage of subjects with newly occurring notable vital signs will be presented. Criteria for notable vital sign abnormalities are provided in Table 2-4 below

Table 2-4 Criteria for notable vital sign abnormalities

Vital sign (unit)	Notable abnormalities
Systolic blood pressure (mmHg)	≥ 140 mmHg or < 90 mmHg
Diastolic blood pressure (mmHg)	≥ 90 mmHg or < 60 mmHg
Pulse (bpm)	> 100 bpm or < 60 bpm

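### For participants who switch from placebo at Week 16, the final lab, ECG and vital-sign abnormality tables keep the pre-placebo baseline and one window across both phases

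*SAP*

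**What the plan says.** **Baseline.** SAP 2.1.1.3: "For safety analyses, baseline is the last assessment (including unscheduled visits) obtained (on or) before the first dose of study treatment". Placebo is study treatment, so for Group 2 this is the Day 1 value before placebo. SAP 2.7.3 repeats the rule for the CTCAE shift tables: "baseline will be defined as last assessment prior to first dosing in initial treatment phase".

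**Window.** SAP 2.7.3 (laboratory), 2.7.4.1 (ECG) and 2.7.4.2 (vital signs) each use a single window, from after the first dose of study treatment to 84 days after the last dose. None is cut at Week 16.

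**Statistic.**
- Laboratory: "Shift tables will be presented comparing baseline laboratory result (CTCAE grade) with the worst results", taken "during the treatment phase (either initial up to week 16 or entire) analyzed".
- ECG: a shift to the "worst on-study interpretation".
- Vital signs: "the number and percentage of subjects with newly occurring notable vital signs will be presented".
- Notable abnormalities: the last row of SAP Table 5-2 takes the most extreme value in the visit window.

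**Period.** SAP 2.7.1: "the data in the period of Entire treatment will be presented at the Final Analysis". Day 1 to Week 16 was reported at the primary endpoint analysis.

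**Columns.** SAP 2.1.1.1: "In the final analysis, the summaries by treatment will be performed by the treatment sequence". Two of the four sequences begin with placebo. The same section allows some safety summaries to use Placebo and Any AIN457 columns instead. SAP 2.7 counts switchers in both groups according to exposure dates. Sections 2.7.3 to 2.7.4 refer only to treatment group and do not say which column set their abnormality tables use.

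**The concern.** Safety and tolerability of secukinumab, including laboratory values and vital signs, is a stated secondary objective, and the final analysis may support regulatory submission (SAP 2.10). For Group 2, the laboratory shift rule offers two phases, Week 0 to 16 and the entire period. Neither is the secukinumab phase alone, and no value at the switch serves as a reference. A reader who wants to know what changed in these participants after they started secukinumab cannot take it from the entire-period worst-value or notable-value tables.

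**Working it through.** The SAP states no figure on this point. The check sets its rules side by side and counts scheduled visits.

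**1. Who is affected.** 40 participants randomized 1:1 gives 20 on placebo. Those who complete Treatment Period 1 start secukinumab at Week 16 (protocol 4.1). They are re-randomized 1:1, so each Placebo – AIN457 sequence holds about 20 / 2 = 10 people. One participant moves a crude percentage in such a column by 1/10 = 10 points.

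**2. Assessments made on placebo.** Protocol 8.4 puts safety assessments before dosing, so Week 16 values belong to the placebo phase. From protocol Table 8-1, for a Group 2 completer:

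| Assessment | On placebo | After first secukinumab dose | Share on placebo |
|---|---|---|---|
| Vital signs | Weeks 1, 2, 3, 4, 8, 12, 16 (7) | Weeks 20 to 52 every 4 weeks, F60 (10) | 7/17 = 41% |
| Hematology, chemistry, urinalysis | Weeks 12, 16 (2) | Weeks 28, 40, 52, F60 (4) | 2/6 = 33% |
| ECG | Week 16 (1) | Week 52, F60 (2) | 1/3 = 33% |

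**3. Three participants under the written rules.** All are in Group 2 with a normal Day 1 value. The SAP does not define newly occurring. I read it as relative to the only safety baseline it gives.

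| Pattern | Sequence column, entire period | By-exposure columns, Day 1 baseline | By-exposure columns, pre-switch baseline |
|---|---|---|---|
| A. Grade 2 at Week 12, normal at Weeks 16 and after | Worst = Grade 2 | Placebo only | Placebo only |
| B. Grade 2 at Week 12, normal at Week 16, Grade 1 at Week 28 | Worst = Grade 2; the later rise is not visible | Placebo 0→2; AIN457 0→1 | Placebo 0→2; AIN457 0→1 |
| C. Grade 2 at Weeks 12, 16 and 28 | Worst = Grade 2 | Placebo 0→2; AIN457 0→2 | Placebo 0→2; AIN457 2→2, no worsening |

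Patterns A and B show the mixing and masking in the sequence columns. Pattern C shows what exposure dates alone do not cure: nothing changed after the switch, yet the participant counts as worsened on secukinumab.

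**4. Table 5-2.** The by-visit safety row has an explicit placebo-to-AIN switch clause. The notable-abnormality row has none.

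**5. Illustration of mixing only.** The documents give no rate of notable vital signs. Assume a per-visit chance p, the same in both phases and independent between visits. The expected number of 20 flagged is 20 × [1 − (1 − p)^17] over the entire period and 20 × [1 − (1 − p)^10] over post-switch visits alone. For p = 1% these are 3.1 and 1.9; for p = 10%, 16.7 and 13.0. Repeated values in one person are unlikely to be independent, so this shows direction and does not estimate an error rate.

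**The case against.** The strongest case is that the SAP labels and separates more than the concern suggests.

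- **Columns.** A reader might infer that abnormalities arising on placebo generally appear in secukinumab columns. The documents do not support that. The default columns name the placebo phase, the AIN457 – AIN457 sequences contain no placebo data, and where Any AIN457 columns are used, SAP 2.7 assigns switchers by exposure dates. A transient placebo finding should then stay under Placebo. This stands.
- **Likely layout.** SAP 2.1.1.1 gives exposure-adjusted summaries as its example for the by-exposure columns, while Table 2-1 plans only crude incidence for lab, ECG and vital-sign notables. Sequence columns are therefore the likelier layout, and pattern C may not arise. But the SAP does not say, and the sequence columns have the mixing problem.
- **Other outputs.** Changes by visit, by-visit laboratory shifts, maximum change within each study period, listings by sequence and the separate Week 16 report allow partial tracing. SAP 5.1.1 also keeps Treatment Period 2 values out of Treatment Period 1. So it would be too strong to say that post-switch effects cannot be recovered. These outputs do not correct the worst-value and notable-value tables.
- **Deliberate choice.** A fixed Day 1 baseline gives all four sequences one reference. That is a fair reason to keep those tables, though not to have them alone.
- **Scope of the wording.** The explicit sentence in 2.7.3 covers only CTCAE shifts. For ECG and vital signs the point rests on the general rule in 2.1.1.3.

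**Conclusion.** The point holds in limited form. For about 20 of 40 participants, the final abnormality tables use a pre-placebo baseline and a window that spans both treatments. In the Placebo – AIN457 columns this mixes the phases and can mask an equal or smaller worsening after the switch. In Any AIN457 columns, if used, the fault is confined to abnormalities that began on placebo and persist past Week 16. Which of the two applies is not stated.

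The supported size is the visit share (7 of 17, 2 of 6, 1 of 3), assuming the planned allocation and full attendance. How many participants would be misattributed cannot be derived from the documents. The effect is on attribution in descriptive tables: SAP 2.7 plans no formal safety testing, and the Week 16 placebo-controlled comparison is untouched. Because the safety objective is explicit and the remedy is small, the change should be made.

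**What to change.** In SAP 2.7.3, 2.7.4.1, 2.7.4.2 and the notable-abnormality row of Table 5-2:

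1. State for each table whether its columns are treatment sequences or Placebo and Any AIN457.
2. For Group 2's secukinumab-phase results in the shift, newly occurring or worsening, and notable-value tables, use only values after the first secukinumab dose, compared with the last value on or before that dose.
3. Report Group 2's Day 1 to Week 16 values under placebo.
4. Add to the notable-abnormality row a switch clause like the one in the by-visit row.

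The Day 1-baseline sequence tables can stay alongside. The cost is SAP wording and one derived baseline variable; pre-dose Week 16 laboratory, ECG and vital-sign data are already scheduled. The drawback is that Groups 1 and 2 then have different reference points, which needs a footnote.

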2.7.4 Other safety data

2.7.4.1 ECG and cardiac imaging data

The summary of ECG will only include treatment emergent data, which are defined as those ECG measurements after the first dose of study treatment and on or before last dose + 84 days.

Analysis in ECG parameters using descriptive summary statistics for the change from baseline for each post-baseline visit will be performed. These descriptive summaries will be presented by ECG parameter and treatment group. Change from baseline will only be summarized for subjects with both baseline and post-baseline values and will be calculated as:

Change from baseline = post-BSL - BSL

The following quantitative variables will be summarized: ECG mean heart rate, RR interval, PR interval, QRS duration, QT interval, and corrected QT interval (QTc). Fridericia (QTcF) corrections will be presented for QTc.

QTc will be summarized by computing the number and percentage of subjects (including 95% confidence intervals for pooled analysis, e.g., DMC or SCS) with:

- QTcF > 500 msec
- QTcF > 480 msec
- QTcF > 450 msec
- QTcF changes from baseline > 30 msec
- QTcF changes from baseline > 60 msec
- PR > 250 msec

Summary statistics will be presented for ECG variables by visit and treatment group.

In addition, shift tables comparing baseline ECG interpretation (normal, abnormal, not available, total) with the worst on-study interpretation (normal, abnormal, not available, total) will be provided.

A listing of all newly occurring or worsening abnormalities will be provided, as well as a by-subject listing of all quantitative ECG parameters.

Qualitative changes will be summarized.

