8.4.2 Electrocardiogram (ECG)

A standard 12 lead ECG will be performed as indicated in Table 8-1. In this study, local electrocardiogram (ECG) will be used. ECGs must be recorded after 10 minutes rest in the supine position to ensure a stable BSL. The preferred sequence of cardiovascular data collection during study visits is ECG collection first, followed by vital signs, and blood sampling.

The original ECGs on non-heat-sensitive paper appropriately signed, must be collected and archived at the study site.

Each ECG tracing must be labeled with study number, subject initials, subject number, date and time, and filed in the study site source documents. Investigator should document clinical evaluation in source. For any ECGs with subject safety concerns, two additional ECGs must be performed to confirm the safety finding

Although there is no exclusion criterion based on ECG results, the BSL ECG at the Randomization Visit must be reviewed locally for major abnormalities prior to dosing.

Clinically significant abnormalities must be recorded on the CRF as either medical history/current medical conditions or adverse events as appropriate.

8.4.3 **Pregnancy and assessments of fertility**

Secukinumab must not be given to pregnant women; therefore effective methods of birth control must be used for women of child-bearing potential for the entire study period (see exclusion criteria definitions, Section 5.2).

All pre-menopausal women who are not surgically sterile will have local urine pregnancy tests, as indicated in Table 8-1. Additional pregnancy testing might be performed if requested by local requirements. A positive urine test requires immediate interruption of study drug and needs to be confirmed with a serum β -hCG test (serum pregnancy test to be done locally). If positive, the participant must be discontinued from the study treatment.

Assessments of fertility

Medical documentation of oophorectomy, hysterectomy, or tubal ligation must be retained as source documents. Subsequent hormone level assessment to confirm the woman is not of child-bearing potential must also be available as source documentation in the following cases:

- 1. Surgical bilateral oophorectomy without a hysterectomy
- 2. Reported 12 months of natural (spontaneous) amenorrhea with an appropriate clinical profile.

| Novartis | | Confidential |
|-------------------------|------------------|--------------|
| Clinical Trial Protocol | (Version No. 00) | |

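### Four absolute ECG rows (QTcF >450, >480, >500 msec; PR >250 msec) ignore baseline, so an interval already above the cut-off that stays there is tabulated as incidence on treatment

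*SAP*

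**What the plan says.** SAP 2.7.4.1 limits the ECG summaries to "treatment emergent data, which are defined as those ECG measurements after the first dose of study treatment", with the window closing 84 days after the last dose. It then lists six categories for which the number and percentage of subjects are reported. Four are absolute: QTcF above 450, 480 and 500 msec (the last written as "QTcF > 500 msec") and PR above 250 msec. Two are relative to baseline: "QTcF changes from baseline > 30 msec" and the same for 60 msec. The absolute rows carry no baseline condition.

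The section also plans change-from-baseline summaries by visit (PR and QTc are among the variables), a baseline-to-worst shift table of the overall reading (normal or abnormal), and a by-subject listing of all quantitative ECG parameters. It adds: "A listing of all newly occurring or worsening abnormalities will be provided".

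Protocol 8.4.2 opens the relevant sentence with "Although there is no exclusion criterion based on ECG results" and goes on to require local review of the baseline ECG for major abnormalities before dosing.

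In SAP Table 2-1 the notables for vital signs and ECG are reported as crude incidence, both to Week 16 and for the entire treatment period. For vital signs, SAP 2.7.4.2 says that "the number and percentage of subjects with newly occurring notable vital signs will be presented". SAP 2.7.3 counts lipid and liver abnormalities only if they are new or have worsened.

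**The concern.** The label, the table type and the counting rule do not fit together. Elsewhere in the same SAP (2.7.1), a treatment-emergent adverse event is one that began after the first dose or was present before and became more severe. In the ECG section the same term means only that the measurement was taken after the first dose. The laboratory and vital-sign sections use the same date window and call it 'on treatment'.

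With no baseline condition, the absolute rows mix findings present at entry (prevalence) with findings that arose on study (incidence), and Table 2-1 presents the result as incidence. The groups are small, so one or two carried-over participants can set the percentage shown. In the final analysis every treatment sequence includes active drug after Week 16, so there is no concurrent placebo rate over that period against which to judge the carry-over.

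**Working it through.** The plan gives no ECG figure to reproduce, so the check is of the counting rule and of what one participant weighs.

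**1. Rules side by side**

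| Safety count | Section | Baseline used? |
|---|---|---|
| Adverse events, treatment emergent | SAP 2.7.1 | Yes: new or more severe |
| Lipid abnormalities | SAP 2.7.3 | Yes: new or worse |
| Liver enzyme abnormalities | SAP 2.7.3, Table 2-3 | Yes: new or worse |
| Notable vital signs | SAP 2.7.4.2 | Yes: new |
| QTcF change >30, >60 msec | SAP 2.7.4.1 | Yes |
| QTcF >450, >480, >500; PR >250 msec | SAP 2.7.4.1 | No |

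**2. The rule applied to illustrative values**

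The values are assumed, because the documents give no ECG distribution. As written: count if post-dose value > cut-off. Newly occurring: count if post-dose value > cut-off and baseline ≤ cut-off.

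| Baseline → post-dose (msec) | Counted as written | Newly occurring | QTcF change row |
|---|---|---|---|
| QTcF 510 → 485 | >450, >480 | none | none (change −25) |
| QTcF 490 → 460 | >450 | none | none (−30) |
| QTcF 470 → 470 | >450 | none | none (0) |
| QTcF 440 → 455 | >450 | >450 | none (+15) |
| PR 270 → 260 | >250 | none | no such row for PR |
| PR 240 → 255 | >250 | >250 | no such row for PR |

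The first three QTcF cases and the first PR case did not worsen, yet all four are counted. The absolute rows cannot tell 470 → 470 from 440 → 455.

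**3. Weight of one participant**

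About 40 are randomized 1:1, giving 20 per arm, and re-randomized 1:1 within arm at Week 16, giving about 10 in each of four sequences (SAP 1.1, 2.1.1.1).

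- Arm: 1/20 = 5 percentage points.
- Sequence: 1/10 = 10 percentage points.
- A pooled column of all participants given active drug, where used: 1/40 = 2.5 percentage points.

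**4. Chance that anyone enters above 450 msec**

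The baseline prevalence p is not in the documents and is assumed here. P(at least one of 40) = 1 − (1 − p)^40:

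- p = 0.02: 0.554
- p = 0.05: 0.871
- p = 0.10: 0.985

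This is the chance that someone enters above 450 msec, so it is an upper bound on the chance that someone enters above it and is still above it post-dose. It says nothing about the 480 and 500 msec rows or PR.

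**5. Whether other outputs separate the cases**

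The shift table uses the overall reading, so a participant abnormal at baseline and on study may or may not have been above a given QTcF or PR cut-off at either time. PR has no categorical change row. The listings show individual values but give no count.

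**The case against.** The strongest reply is that nothing is hidden. The same section plans change summaries that include PR, two QTcF change rows, a listing of new or worsened abnormalities, and every participant's ECG values. With about 40 participants and scheduled post-baseline ECGs only at Weeks 16, 52 and F60, a reader can find who was above a cut-off at entry. The date window is stated openly, and the rows are described as numbers of subjects above a value, not as events. Safety is descriptive, with no formal testing (SAP 2.7), and up to Week 16 randomization balances pre-existing cases on average. All of this stands. It limits the defect to four tabulated rows and their label, but it does not make those rows incidence.

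Three stronger readings are tempting and not supported:

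- **That the ECG table cannot show on-treatment change.** The QTcF change rows in the same list do show it.
- **That participants with markedly prolonged intervals will enter freely.** The baseline ECG must be reviewed for major abnormalities, and exclusion criteria 15 and 16 cover some cardiac conditions. Neither sets a QTcF or PR limit, so entry above a cut-off is possible, but its frequency is unknown.
- **That every improved interval is miscounted.** An improved interval is counted only if it stays above the cut-off.

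A caution applies to the remedy too. Simply requiring baseline at or below the cut-off would remove real worsening: QTcF 505 → 560 msec would leave the >500 row and appear only under change >30, and PR 255 → 320 msec would leave every count.

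**Conclusion.** The point holds for the four absolute rows only. As written, they count a stable or improved interval that remains above the cut-off, under a treatment-emergent label and in a table of crude incidence, contrary to the SAP's own practice for vital signs, lipids and liver enzymes. Each such participant adds about 5 points in an arm of 20 or about 10 in a sequence of 10, assuming the planned allocation is met. How many there will be cannot be derived from the documents; the 55% to 98.5% range for at least one entrant above 450 msec rests wholly on assumed prevalences of 2% to 10%.

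This is a minor point of descriptive safety reporting. It affects no estimand or success criterion, and the individual data remain traceable. It is worth correcting because this SAP governs the final analysis, where the entire-treatment ECG counts are to be reported.

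**What to change.** In SAP 2.7.4.1:

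1. Call the data window 'on treatment', as the laboratory and vital-sign sections do.
2. Keep the four absolute rows, but split each, using the highest post-dose value in the window, into:
   - (a) newly above the cut-off (baseline at or below it);
   - (b) already above at baseline and worse post-dose;
   - (c) already above at baseline and not worse.
3. Show the number above each cut-off at baseline beside the row, and any participant without a baseline ECG on a separate line.
4. Report (a) + (b) as the new-or-worsened count, in line with the lipid and liver tables.
5. Keep the QTcF >30 and >60 msec change rows, which show the size of a rise.

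Under this split QTcF 510 → 485 falls in (c) of the >450 and >480 rows, and 460 → 485 in (b) of >450 and (a) of >480. QTcF 505 → 560 falls in (b) of all three QTcF rows, and PR 255 → 320 in (b). No worsening is lost and no stable value passes as new.

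The cost is a few lines of SAP wording and a small programming change. Baseline ECGs are already collected, so no new data are needed.
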